4.2.5 Data Listings

All listings will contain information both for arm A and arm B (arm A patients followed by arm B patients). Patients who change treatment in arm A after radiological progression at week 8 will be flagged.

All listings will include scheduled and unscheduled measurements. All listings will display the same number of decimals as in the source data. All raw data will be reported exactly as provided.

4.2.6 Data summaries

Summaries will be presented as follows:

- Arm A and arm B in the same table, as detailed described in the following sections. A separate set of tables and figures on selected endpoints will be done for arm A1 and/or arm A2.
- No formal comparisons will be performed between arms.

4.2.7 Figures

Figures for efficacy evaluation will be produced as detailed in Section 4.11. In selected presentations where specified, figures presenting arm A, arm A1, arm A2 and arm B will be produced. For arm A1 and arm A2, KM curves will be presented provided there enough data to make it meaningful to do so: at least 8 events.

4.2.8 Handling of Dropouts or Missing Data

There will be no imputation of missing data, unless otherwise stated.

4.2.9 Analysis Conventions

Continuous data will be summarized in terms of the mean, standard deviation, median, minimum, maximum and number of observations, unless otherwise stated.

The minimum and maximum will be reported to the same number of decimal places as the raw data recorded in the database. The mean and median, will be reported to one more decimal place than the raw data recorded in the database. The standard deviation will be reported to two more decimal places than the raw data recorded in the database. In general, the maximum number of decimal places reported shall be four for any summary statistic.

Categorical data will be summarized in terms of the number of patients providing data at the relevant time point (n), frequency counts and percentages. Any planned collapsing of categories will be detailed in the SAP text and the data displays.

Percentages will be presented to one decimal place. Percentages will not be presented for zero counts. Percentages will be calculated using n as the denominator.

Changes from baseline in categorical data will be summarized using shift tables where appropriate.

Confidence intervals will be presented to one more decimal place than the raw data.

4.3 Software

TFLs and any non-descriptive statistical analysis will be produced using SAS® Software (Version 9.3 or higher). The REPORT procedure (SAS PROC REPORT) will be used to produce all table and listings; SAS/GPGRAPH will be used to produce all figures.

4.4 Study Patients

4.4.1 Disposition of Patients

A clear accounting of the disposition of all patients who enter the study will be provided from screening to study completion.

The number of patients who were screened (who signed main study ICF), were exposed to study treatment, who completed the study or discontinued and primary reason for end of treatment will be summarized for arm A and arm B in the FAS. The number of patients in arm A who switch from monotherapy to combination therapy will also be summarized. The number of patients in arm A and arm B who remained on original treatment despite disease progression will also be presented.

The patient disposition including the date the informed consent was signed, date of first/last intake of study drug and the primary reason for End of Treatment will be listed.

A listing of patients included into each of the analysis set will be presented, related summary statistics will be provided. Patients who did not meet the eligibility criteria or were screen failures will also be listed.

4.4.2 Protocol Deviations

Deviations from the protocol including violations of inclusion/exclusion criteria will be assessed as “minor” or “major” in cooperation with the Sponsor in an ongoing manner during protocol deviation review meetings. Major protocol deviations are defined as those deviations from the protocol likely to have an impact on the perceived efficacy and/or safety of study treatments. Protocol deviations are defined in the project-specific Protocol Deviation Specification. Whether a protocol deviation results in exclusion from a particular analysis set will be detailed in the protocol deviation specification and documented in the supporting protocol deviation review document.

The number and percentage of patients with major protocol deviations will be summarized by type of deviation for arm A and arm B in the FAS. The summary will be done separately for major protocol deviations leading to exclusion from the evaluable set and the other major protocol deviations. All protocol deviations will be listed.

4.5 Analysis Sets

A summary of the number of patients included in each analysis population described below will be provided for arm A and arm B. Percentage of subjects in the evaluable set will be calculated based on the full analysis set (FAS).

A listing of patients included into each of the analysis set will be presented will be provided. The patients who did not meet the eligibility criteria or were screen failures will also be listed.

- **Full analysis set (FAS) / Safety analysis set:** All patients who enrolled and received at least one dose of study drug (RXC004 in the case of the monotherapy arm and at least one of RXC004 or nivolumab in the combination arm).

- CCI [REDACTED]

- **PK analysis set:** All patients in the safety analysis set who have had at least 1 blood sample.

4.6 Demographics and Baseline Characteristics

Demographic and Baseline characteristics will be summarized and listed for the FAS.

Demographics will be summarized for arm A and arm B, including:

- Age (years)
- Gender (Male or Female)
- Race (American Indian or Alaska Native, Asian, Black or African, American, Native Hawaiian or Other Pacific Islander, White, Other)
- Ethnicity (Hispanic or Latino, Not Hispanic or Latino, Not Stated, Unknown)

Baseline characteristics will be summarized for arm A and arm B, including:

- Weight (kg)
- Height (only screening visit) (cm)
- Body Mass Index (BMI) result (kg/m²)
- ECOG PS at Study Entry
- Stage at Study Entry
- Primary Location
- Cancer Classification (Histology)
- Histological Grade
- TNM status
- MSI status
- WNT pathway genetic aberration (LoF RNF43 mutation, RSPO2/3 Fusion, Wild Type, No Results Available)
- PD-L1 Tumor proportion score: as continuous and categorical variable (<1%, >=1% - 49%, >50%)
- PD-L1 Immune proportion score: as continuous and categorical variable (<1%, >=1% - 49%, >50%)
- Site of Local/Metastatic Disease
- Number of prior lines of cancer therapy and indications
- Best response achieved for the most recent treatment
- Time from last Disease Progression disease to first dose of Study Drug (weeks)*
- Time from Initial Metastatic Diagnosis to first dose of Study Drug (Months)*
- Time from last most recent Dose of prior therapy to first dose of Study Drug (weeks)*
- Sum of target lesions at Baseline

(*) In case, last disease progression date, initial metastatic diagnosis date or most recent dose prior therapy date is incomplete, the following imputation rules will be implemented:

- UK-MMM-YYYY: Assume 01-MMM-YYYY.
- UK-UKN-YYYY: If the year is prior to the year of first dose of study drug, assume 01-JUL-YYYY of the collected year. Otherwise, no imputation.
- UK-UKN- UNKN: No imputation. Duration will be considered as missing.

4.7 Medical History and Surgical History

Medical history and Surgical history as pre-specified in the Medical and Surgical history eCRF will be presented in the patient data listings.

4.8 Prior and Concomitant Medications

Prior and concomitant medications will be coded using the World Health Organization - Drug Dictionary (WHO-DD) Version March 2023 and will be classified by Anatomical Therapeutic Chemical (ATC) categories. Prior medications will be defined as medications that stopped before the first dose of study drug and will be listed only.

For the purpose of categorizing medications as prior or concomitant, incomplete medication start and stop dates will be imputed as follows:

Missing start dates (where UK, UKN and UNKN indicate unknown or missing day, month and year respectively):

- UK-MMM-YYYY: Assume 01-MMM-YYYY. If the month and year are the same as the first dose of study drug month and year, then assume the date of first dose of study drug;
- UK-UKN-YYYY:
 - If the year is prior to the year of first dose of study drug, assume 01-JUL-YYYY of the collected year. If the end date is before 01-JUL-YYYY, assume the first day of the year.
 - If the year is the same as the first dose of study drug year, then assume the date of first dose of study drug. If the End Date occurs before the first dose of study drug, then assume the first day of the year.
 - If the year is after the first dose of study drug year, then assume the first day of the year.
- UK-UKN- UNKN: Assume date of first dose of study drug. In case end date is before first dose of study drug, assume the first day of the year of the CM end date.

Missing stop dates for concomitant medications data will be handled as follows (where UK, UKN and UNKN indicate unknown or missing day, month and year respectively):

- UK-MMM-YYYY: Assume the last day of the month;
- UK-UKN-YYYY: Assume 31-DEC-YYYY;
- UK-UKN- UNKN: Assume ongoing and leave it missing.

Medications will be categorized as follows:

Medication start and stop dates will be compared to the date of first dose of study medication to allow medications to be classified as either Prior or Concomitant.

Medications and treatments administered prior to the Investigational Medicinal Product (IMP) intake which stopped prior to IMP intake will be considered as prior medications. Medications and treatments which started before, on or after the IMP intake and which stopped after IMP intake of study drug (including medications and treatments which stopped the day of the IMP intake) will be considered as concomitant medications. If medication start and/or stop dates are missing or partial, the dates will be compared as far as possible with the date of IMP dosing. Medications will be assumed to be concomitant, unless there is clear evidence (through comparison of partial dates) to suggest that the medication stopped prior to the IMP dosing. If there is clear evidence to suggest that the medication stopped prior to the IMP dosing, the medication will be assumed to be Prior.

Medications and treatments with a start date after the last dose of IMP will be considered as post-study medication and will not be considered as concomitant medications.

Concomitant medications will be analysed for arm A and arm B for the FAS.

The number (n) and percentage (%) of patients taking concomitant medications will be summarized by ATC classification and Preferred Name. ATC Level 1 will be sorted by alphabetical order. Preferred Names, within each ATC Level 1, will be sorted by descending frequency of the total frequency. In the event of Preferred Names with equal total frequencies, the relevant Preferred Names will be sorted alphabetically. Similarly, if a patient reported more than one concomitant or post-treatment medication within the same primary ATC Level 1, the patient will be counted only once. Prior and concomitant medications (ATC Level 1/ Preferred Name), dose, frequency and route, start/stop date (or ongoing) and type of indication as specified in the eCRF with medication category (Prior or Concomitant) will be presented in the by- patient data listing for FAS.

Additional summaries and listing will be created specifically for Prior anti-cancer therapies.

4.9 Prior and Concomitant Radiotherapy and Procedure

Prior and concomitant radiotherapy will be summarized and listed for the FAS.

The following prior radiotherapy variables will be described:

- Number of patients having a history of radiotherapy
- Intent of prior radiotherapy
- Sites of prior radiotherapy

The following concomitant radiotherapy variables will be described:

- Number of patients having a concomitant radiotherapy
- Intent of concomitant radiotherapy
- Sites of concomitant radiotherapy

Concomitant procedure will be listed for the FAS.

4.10 Extent of Exposure

FAS population set will be considered for the analysis. Extent of exposure will be summarized for arm A and arm B. The below derived parameters will be listed by arm and patient.

4.10.1 RXC004

Duration and compliance of the RXC004 exposure will be assessed by computing the following variables:

- Number of cycles and number of doses per patient
- RXC004 Duration of treatment (weeks) = (Date of last dose – Date of first dose + 1) / 7
- Cumulative dose (mg) = Sum of all doses administered
- RXC0004 RDI (%) = [Cumulative dose received (mg) / (RXC004 Duration of treatment (days) * 2mg)] * 100, for Arm A
- RXC0004 RDI (%) = [Cumulative dose received (mg) / (RXC004 Duration of treatment (days) * 1.5mg)] * 100, for Arm A combination and Arm B

For switching patients in arm A, RXC0004 RDI for Arm A combination should be considered from the start of the combination.

- Number of patients with dose reduced and reason for reduction
- Number of patients with dose interrupted and reason for interruption

Duration of the RXC004 duration, and Cumulative dose will be summarized as continuous variables. RDI will be summarized as continuous variable and by categories:] - ; 60%[, [60% ; 75%[, [75% ; 90%[, [90% ; 100%],] 100% ; +].

The number of patients who had dose reductions will be summarized by categories: (Any, 1, 2 times).

Another summary will be produced excluding treatment cycles after the progression for the patients who remain on treatment despite PD. A swimmer plot will be produced presenting the duration of treatment. A tag will show the first PD and when patients achieve response. For the patients in arm A who switched to combination, a different colour will be used for the monotherapy and the combination treatment. Swimmer plots will be presented separately for arm A and arm B

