## 1.2 Schedule of Assessments

**Table 1** Arm A Schedule of Assessments

Treatment Phase	Table 1 – Arm A Schedule of assessments											
	Pre-treatment		RXC004 monotherapy			RXC004 + nivolumab combination j		Post-treatment				
	Pre-Screening	Screening	Cycle 0 (3-7 days)	Cycle 1 (28 day cycle)		Cycle 2 onwards (28 day cycles)	Pre-first Cycle	Cycle 1 onwards (28 day cycles)	IP Discontinuation	30 day Follow-up v	90 day Follow-up v	Survival follow-up
Window	n/a	-28 to -1	D1	D1	D15 +/- 1d	D1 +/- 3d		D1 +/- 3d	Within 7 days	+/- 3d	+/- 3d	q8w +/- 1wk
Pre-Screening informed consent	X											
CCI CCI CCI	X											
Genetic screening for RNF43/RSPO aberrations and MSI status t	X											
Main study informed consent		X										
Demography & baseline characteristics		X										
Smoking history		X										
Central MSI testing (if not completed in pre-screening)		X										

Table 1 – Arm A Schedule of assessments

Treatment Phase	RXC004 monotherapy											RXC004 + nivolumab combination j				Post-treatment			
	Pre-treatment		Cycle 0 (3-7 days)			Cycle 1 (28 day cycle)		Cycle 2 onwards (28 day cycles)		Pre-first Cycle	Cycle 1 onwards (28 day cycles)		IP Discontinuation	30 day Follow-up v	90 day Follow-up v	Survival follow-up			
Window	Pre-Screening	Screening	D1	D1	D15 +/- 1d	D1 +/- 3d		D1 +/- 3d	Within 7 days	+/- 3d	+/- 3d	q8w +/- 1wk							
CCI																			
CCI																			
CCI																			
CCI																			
CCI																			
CCI																			
CCI																			
CCI																			
Medical/ surgical history		X																	
Oral and dental assessment w		X	Oral assessment at each visit - only if patient reports dysgeusia																
Inclusion/ exclusion criteria		X						X k											
HepB, HepC and HIV testing		X																	

Table 1 – Arm A Schedule of assessments

Treatment Phase	Table 1 – Arm A Schedule of assessments											
	Pre-treatment		RXC004 monotherapy				RXC004 + nivolumab combination j		Post-treatment			
	Pre-Screening	Screening	Cycle 0 (3-7 days)	Cycle 1 (28 day cycle)		Cycle 2 onwards (28 day cycles)	Pre-first Cycle	Cycle 1 onwards (28 day cycles)	IP Discontinuation	30 day Follow-up v	90 day Follow-up v	Survival follow-up
Window	n/a	-28 to -1	D1	D1	D15 +/- 1d	D1 +/- 3d		D1 +/- 3d	Within 7 days	+/- 3d	+/- 3d	q8w +/- 1wk
CCI												
CCI												

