RECIST 1.1 assessments (by CT/MRI) n		X		On study tumour assessments should occur q8w +/- 1 week (relative to first dose of IP) for the first 56 weeks, followed by q12w +/- 1 week until RECIST1.1 radiological progression x				On study tumour assessments should continue q8w +/- 1 week (relative to first dose of IP) for the first 56 weeks, followed by q12w +/- 1 week until RECIST1.1 radiological progression q, x				If a patient discontinues for a reason other than progression then tumour assessments should continue q8w +/- 1 week (relative to first dose of IP) for the first 56 weeks, followed by q12w +/- 1 week until RECIST1.1 radiological progression					
CCI h (mandatory unless unavailable at site) i		X*		On study CCI h assessments should occur at week 8 and week 16 +/- 1 week relative to first dose of IP.			On study CCI h assessments should occur at week 8 and week 16 +/- 1 week relative to first dose of combination										
Vitamin D3 and Calcium supplements			Patients should commence 800 IU vitamin D3 (Cholecalciferol) daily and 1000-1500 mg calcium daily supplements from ICF signature until RXC004 discontinuation														
Denosumab dosing y			120 mg sc Denosumab once every month from C0D1 until RXC004 discontinuation														
RXC004 dosing m			X (2 mg single dose)	Continuous daily dosing (2 mg QD)			Continuous daily dosing (1.5 mg QD)										
RXC004 diary			X	Review at each visit													

Table 1 – Arm A Schedule of assessments

Treatment Phase	Pre-treatment		RXC004 monotherapy			RXC004 + nivolumab combination j		Post-treatment				
	Pre-Screening	Screening	Cycle 0 (3-7 days)	Cycle 1 (28 day cycle)		Cycle 2 onwards (28 day cycles)	Pre-first Cycle	Cycle 1 onwards (28 day cycles)	IP Discontinuation	30 day Follow-up v	90 day Follow-up v	Survival follow-up
Window	n/a	-28 to -1	D1	D1	D15 +/- 1d	D1 +/- 3d		D1 +/- 3d	Within 7 days	+/- 3d	+/- 3d	q8w +/- 1wk
Nivolumab dosing								480 mg q4w +/- 3 days o				
RXC004 PK f			X		X	X		X	X			
Concomitant medication		X	X	X	X	X	X	X	X	X	X	
Adverse events		X	X	X	X	X	X	X	X	X	X	
Taste assessment z		X	At each visit – only if patient reports dysgeusia									
Survival status and post-discontinuation anti-cancer therapy p										X	X	X

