4.2.1 Study Days

Screening will be conducted between Day -28 and Day -1. The first day of treatment will be Cycle 0 - Day 1 (C0D1). When calculating AEs/ConMeds/etc timing days will be calculated relative to day 1.

For patients in arm A, who have radiologically progressed at Week 8 and move to RXC004 + Nivolumab, count of days will re-start from the day of the first of intake of the combination a new Cycle 1 with D1, as reported in the Schedule of Activities (SoA) (see protocol).

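### The RXC004 dose intensity formula counts planned dose-free Cycle 0 days at the full daily dose, so fully adherent patients in Arms A and B who continue past C0D1 score below 100%

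*SAP*

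**What the plan says.** SAP 4.10.1 builds the RXC004 exposure measures from three definitions:

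- duration: "RXC004 Duration of treatment (weeks) = (Date of last dose – Date of first dose + 1) / 7"
- cumulative dose: "Cumulative dose (mg) = Sum of all doses administered"
- RDI for Arm A: "RXC0004 RDI (%) = [Cumulative dose received (mg) / (RXC004 Duration of treatment (days) * 2mg)] * 100, for Arm A"

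A second RDI formula has 1.5 mg per day in the denominator; it ends "1.5mg)] * 100, for Arm A combination and Arm B". For patients who switch from monotherapy, the section adds that "RXC0004 RDI for Arm A combination should be considered from the start of the combination". RDI is summarised as a continuous variable and in bands cut at 60%, 75%, 90% and 100%.

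SAP 4.2.1 fixes the start of the clock: "The first day of treatment will be Cycle 0 - Day 1 (C0D1". In the protocol's Section 1.2, the Arm A schedule (Table 1) has a column headed "Cycle 0 (3-7 days", and its RXC004 dosing row reads "X (2 mg single dose" for that cycle. Continuous daily dosing begins in Cycle 1. The Arm B schedule (Table 2) has the same structure at 1.5 mg.

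**The concern.** An RDI should equal 100% when a patient receives exactly what was planned. Here the numerator holds one dose for Cycle 0, while the denominator holds a full daily dose for each of its 3 to 7 days. The shortfall comes from the schedule and not from the patient.

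The SAP adjusts for the dosing schedule elsewhere. Its visit windows (4.2.2) are anchored on C1D1 because of the gap after C0D1, and nivolumab duration (4.10.2) adds 28 days to cover the dosing interval. The RXC004 RDI has no such adjustment.

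The effect is largest in patients who stop early. Protocol 2.3.3 quotes a median PFS of about 2 months for third-line standard agents, and the first scan is at week 8. If treatment is similarly short here, which is an assumption, many patients will sit where the distortion is greatest. With about 20 evaluable patients per arm, one patient in the wrong band moves a category percentage by about 5 points (1/20).

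**Working it through.** The SAP states no numerical RDI, so there is no figure to reproduce. The formula can be applied directly to a patient who misses nothing.

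**Inputs.** C0 is the length of Cycle 0, 3 to 7 days, with one planned dose (Protocol Tables 1 and 2). d is the number of daily doses from C1D1 to the last dose; the values used are illustrative. Duration is last dose minus first dose plus 1, with the first dose at C0D1 (SAP 4.10.1 and 4.2.1).

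**Formula.** Dose received = (1 + d) × daily dose. Denominator = (C0 + d) × daily dose. The daily dose cancels, so Arm A and Arm B give the same result:

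RDI = 100 × (1 + d) / (C0 + d)

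| Daily doses d | 3-day Cycle 0 | 7-day Cycle 0 |
|---|---|---|
| 14 | 15/17 = 88.2% | 15/21 = 71.4% |
| 28 | 29/31 = 93.5% | 29/35 = 82.9% |
| 56 | 57/59 = 96.6% | 57/63 = 90.5% |
| 84 | 85/87 = 97.7% | 85/91 = 93.4% |
| 168 | 169/171 = 98.8% | 169/175 = 96.6% |

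**SAP bands, fully adherent patient.** With a 7-day Cycle 0:

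- 1 to 7 daily doses: below 60% (7 doses: 8/14 = 57.1%)
- 8 to 16: 60% to under 75% (8 doses: 9/15 = 60.0%)
- 17 to 52: 75% to under 90% (17 doses: 18/24 = 75.0%)
- 53 or more: 90% and above (53 doses: 54/60 = 90.0%)

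With a 3-day Cycle 0, 90% is reached at 17 daily doses (18/20).

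**One missed dose.** With a 7-day Cycle 0 and 56 scheduled daily doses, missing one gives 56/63 = 88.9%, in the band below 90%. Against the planned dose it is 56/57 = 98.2%.

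**At the first scan.** Scans are timed from the first dose. A patient whose last dose is on day 56 from C0D1 has taken 57 − C0 doses in 56 days. For Cycle 0 of 3, 4, 5, 6 and 7 days this gives 96.4%, 94.6%, 92.9%, 91.1% and 89.3%.

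**Cases that are not affected.** A patient who takes only the C0D1 dose has a duration of 1 day and scores 100%. The Arm A combination RDI starts with daily dosing and has no Cycle 0, so an adherent patient scores 100% there too.

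**Switchers, if the 2 mg formula were run to the last RXC004 dose.** Take 8 weeks at 2 mg and 16 weeks at 1.5 mg, with no break between phases. Leaving Cycle 0 aside: (8 × 2 + 16 × 1.5) / (24 × 2) = 40/48 = 83.3%. With a 7-day Cycle 0: (2 × 57 + 1.5 × 112) / (2 × 175) = 282/350 = 80.6%.

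**The case against.** The best defence is that little depends on this number. RDI is descriptive, no formal comparison of the arms is planned, and the tolerability endpoint (AEs, SAEs, dose reductions, interruptions, discontinuations and dysgeusia) does not include it. Reductions and interruptions are counted separately with reasons. Number of doses, duration and cumulative dose are listed by patient, so a reader can see that a low RDI came with no interruption. Both arms share the same Cycle 0 structure. At day 56 from C0D1 only the longest Cycle 0 takes an adherent patient below 90%, and the documents give no distribution of Cycle 0 lengths. All of this stands, and it limits the consequence. It does not make the formula right.

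A reader might infer more than the text supports in two ways:

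- **That the SAP scores a switcher's 1.5 mg period against 2 mg.** It does not say so. It provides a separate 1.5 mg RDI counted from the start of the combination, and the natural reading is two phases, each against its own dose. What is missing is a statement that the 2 mg calculation stops at the switch. Duration is defined to the last dose, and SAP 4.2.3 puts information on all Arm A patients into Arm A. That is an ambiguity and not a stated rule; 83.3% and 80.6% arise only on the literal reading.
- **That adherent patients are labelled as dose-reduced, or that the tolerability findings are compromised.** The bands are unlabelled numbers, and SAP 4.10.1 presents these variables as measures of duration and compliance.

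**Conclusion.** The point holds for Cycle 0 in Arms A and B. As written, the rule gives an RDI below 100% to any fully adherent patient who continues past C0D1. The shortfall after 28 daily doses is 6.5 to 17.1 percentage points (93.5% to 82.9%), and after 56 it is 3.4 to 9.5 points (96.6% to 90.5%), depending on Cycle 0 length. It shrinks further with time on treatment. It can place short-treated adherent patients one or more bands too low.

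The result rests on the protocol's planned Cycle 0 of 3 to 7 days with one dose, on C0D1 being the date of first dose, and on illustrative treatment lengths. It concerns a descriptive compliance summary and leaves the primary endpoints untouched. The switcher question needs only a clarifying sentence.

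**What to change.** Define RDI as cumulative dose received divided by cumulative dose planned, times 100. Planned dose is one Cycle 0 dose plus the days of scheduled daily dosing, up to the last dose, times the arm's protocol starting dose. Dose reductions and missed doses then still lower the RDI, and every fully adherent patient scores 100%.

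Count scheduled daily dosing from the earlier of actual C1D1 and the day after the protocol's 7-day maximum Cycle 0, that is, day 8 from C0D1. Without this cap, a long hold after the first dose would be excused. For example, with C1D1 on day 15 and 28 daily doses taken, the last dose is on day 42. Planned doses are 1 + 35 = 36, and RDI is 29/36 = 80.6%. Counting from actual C1D1 would give 29/29 = 100%.

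Add one sentence that for switchers the Arm A (2 mg) RDI uses dose and duration only up to the last monotherapy dose. Use the same denominator in the additional summary that drops cycles after progression.

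The cost is SAP wording and a minor programming change.
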